### APPENDIX 3. INTERNATIONAL MYELOMA WORKING GROUP RESPONSE CRITERIA, MYELOMA

**Table 10: International Myeloma Working Group Response Criteria (Kumar 2016)**

Standard IMWG Response Criteria 	
Response Subcategory	Response Criteria
Complete response (CR)	Negative immunofixation of serum and urine, disappearance of any soft tissue plasmacytomas (SPDs), and < 5% plasma cells in bone marrow aspirates
Stringent complete response (sCR)	CR as defined above plus normal FLC ratio  and absence of clonal cells in bone marrow biopsy by immunohistochemistry ( $\kappa/\lambda$ ratio $\leq 4:1$ or $\geq 1:2$ for $\kappa$ and $\lambda$ patients, respectively, after counting $\geq 100$ plasma cells  )
Very good partial response (VGPR)	Serum and urine M-protein detectable by immunofixation but not on electrophoresis or $\geq 90\%$ reduction in serum M-protein plus urine M-protein level < 100 mg per 24 hr
Partial response (PR)	$\geq 50\%$ reduction of serum M-protein plus reduction in 24-hr urinary M-protein by $\geq 90\%$ or to < 200 mg/24 hr. If the serum and urine M-protein are not measurable, a $\geq 50\%$ decrease in the difference between involved and uninvolved FLC levels is required in place of the M-protein criteria. If serum and urine M-protein and serum FLC assay are not measurable, $\geq 50\%$ reduction in plasma cells is required in place of M-protein, provided baseline bone marrow plasma cell percentage was $\geq 30\%$ . In addition to the above criteria, if present at baseline, a $\geq 50\%$ reduction in the size (SPD) of soft tissue plasmacytomas is also required. 
Minimal response (MR)	$\geq 25\%$ but < 49% reduction of serum M-protein and reduction in 24-hr urine M-protein by 50–89%. In addition to the above criteria, if present at baseline, a $\geq 50\%$ reduction in the size (SPD) of soft tissue plasmacytomas is also required. 
Stable disease (SD)	Not recommended for use as an indicator of response; stability of disease is best described by providing the TTP estimates. Not meeting criteria for CR, VGPR, PR, MR, or PD.
Progressive disease (PD) 	Any 1 or more of the following criteria: Increase of 25% from lowest confirmed response value in 1 or more of the following criteria: Serum M-protein with absolute increase of $\geq 0.5$ g/dL;

Standard IMWG Response Criteria	
Response Subcategory	Response Criteria

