-  Positive immunofixation alone in a patient previously classified as achieving a CR will not be considered progression. For purposes of calculating time to progression and PFS, patients who have achieved a CR and are MRD-negative should be evaluated using criteria listed for PD. Criteria for relapse from a CR or relapse from MRD should be used only when calculating disease-free survival.
-  In the case where a value is felt to be a spurious result per Investigator discretion (e.g., a possible laboratory error), that value will not be considered when determining the lowest value.

Questions regarding interpretation of these criteria may be addressed by consulting the, “Practical considerations for application of IMWG consensus criteria,” section of the guidelines (page e340, [Kumar 2016](#)).

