4. EFFICACY

Patient response at each time point will be assessed centrally by an IRC according to the IMWG response criteria (*Kumar 2016*) for MM. Unless otherwise specified, MM response assessment refers to assessment determined by IRC. The primary endpoint (ORR) is based on these IRC assessed responses in the mITT population.

Documentation of response requires two consecutive readings of the applicable disease parameter (serum M-protein, urine M-protein, serum FLC, or quantitative immunoglobulin level), performed at any time with no minimum interval required between the two readings. The date of response or PD will be assigned to the earlier date of the two independent samples, unless PD is based on an unambiguous criterion such as a new plasmacytoma lesion.

If a patient had one PD assessment but was not subsequently confirmed, unless IRC considers the progression assessment unambiguous, it is not considered a PD (*Kumar 2016*).

Unless otherwise specified, efficacy analyses will use the mITT population. Analyses for the primary efficacy endpoint of ORR and the key secondary efficacy endpoints of DOR, CBR, and duration of clinical benefit will be repeated in the other efficacy populations and additional analysis populations. If relevant, selected efficacy analyses for other efficacy endpoints will be repeated in selected additional analysis populations.

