4.2.2. Best Overall Response and Clinical Benefit Rate (CBR)

4.2.2.1. Definition

The number and percentage of patients in the individual response categories (MR, PR, VGPR, CR, sCR) based on best response will be calculated respectively.

CBR is defined as the proportion of patients who achieve a confirmed MR or better, i.e., MR, PR, VGPR, CR, sCR. Duration of clinical benefit is defined as the duration from first observation of at least MR to time of IRC-determined PD or death due to disease progression, whichever occurs first. Responders without IRC-determined PD or death due to disease progression will be censored at the censored date for TTP.

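### Minimal response in Table 10 is capped in serum and in urine and does not meet partial response, so some patients above the MR range are literally stable disease and outside CBR

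*Protocol*

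**What the plan says.** **Protocol Appendix 3, Table 10.**

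- PR: at least 50% "reduction of serum M-protein plus reduction in 24-hr urinary M-protein by" at least 90%, with the urine alternative of a fall to below 200 mg/24 hr.
- MR: at least 25% "but < 49% reduction of serum M-protein and reduction in 24-hr urine M-protein by 50–89" percent. Both parts have a ceiling, and the two are joined by a plain conjunction.
- SD: "Not meeting criteria for CR, VGPR, PR, MR, or PD".
- PR and MR carry the same further condition on soft tissue plasmacytomas, so that condition does not separate them.

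The table is headed and sourced as the international consensus criteria of 2016. A closing note deals with unclear cases: "Questions regarding interpretation of these criteria may be addressed by consulting the" guideline's section on practical application.

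**SAP section 4.** "Patient response at each time point will be assessed centrally by an IRC according to the IMWG response criteria". The section names CBR and duration of clinical benefit among the key secondary endpoints and repeats them in the other analysis populations.

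**SAP 4.2.2.1.** "CBR is defined as the proportion of patients who achieve a confirmed MR or better".

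**SAP 4.2.7.2 and 4.2.8.2.** The boundary between MR and SD also sets the best-response groups for overall survival (MR or better, MR, SD or worse) and one of the quality-of-life summaries (MR or better).

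**The concern.** Response categories should be ordered: a patient who improves more should not land in a lower category. Two features of the MR row break this. Its upper limits stop short of where PR begins. It also caps both compartments, although PR demands both compartments at once, so a patient can be too good for MR in one and not good enough for PR in the other. Because SD is an explicit residual, this is a stated rule with a misordered result, not a missing detail.

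At stake are CBR, duration of clinical benefit and the summaries by best response. On the literal text every misplaced patient moves down. Such a patient drops out of CBR, or enters it only on later reaching PR (so the benefit clock starts later), or joins the SD-or-worse group in the survival summary. No patient moves up.

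**Working it through.** **1. The plan's own figure.** Protocol Table 3 (Part 1, 78 patients) gives 4 VGPR, 12 PR and 10 MR. ORR count = 4 + 12 = 16. CBR count = 16 + 10 = 26. CBR = 26/78 = 33.3%, matching the stated 33% (exact 95% CI 23.1% to 44.9%). This serves only as a scale: Table 3 is dated 1 December 2016, and the change log places the move to the 2016 criteria in protocol version 4.1, dated 6 February 2017.

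**2. Literal classification under Table 10** (other PR and MR conditions assumed met, no progression):

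| Serum fall | Urine fall | Baseline to residual urine (mg/24 hr) | Category |
|---|---|---|---|
| 30% | 55% | any | MR |
| 30% | 70% | any | MR |
| 53% | 65% | 2000 to 700 | SD |
| 60% | 70% | 1000 to 300 | SD |
| 60% | 70% | 500 to 150 | PR |
| 40% | 95% | any | SD |
| 49.5% | 70% | any | SD |
| 30% | 89.5% | any | SD |

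The 53%/65% and 40%/95% patients improve more in both compartments than the 30%/55% patient, yet rank lower.

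**3. How wide the gap is.** With serum down at least 50%, the urine alternative "or to < 200 mg/24 hr. If the serum and urine M-protein are not measurable" rescues many patients to PR. The gap remains only if residual urine is at least 200 mg/24 hr, that is, baseline ≥ 200/(1 − urine fall):

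- urine fall 50%: 200/0.50 = 400 mg/24 hr
- urine fall 70%: 200/0.30 = 667 mg/24 hr
- urine fall 89%: 200/0.11 = 1,818 mg/24 hr

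This side of the gap therefore needs substantial baseline urinary protein. The other side (serum 25% to below 49%, urine at least 90%) has no such escape, because PR fails on serum whatever the urine residual.

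**4. Size.** The documents give no serum and urine values by patient, so no corrected CBR can be computed. Let k be the number of patients moved from SD to MR.

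| k | Part 1 CBR, (26 + k)/78 | Part 2 shift, k/122 |
|---|---|---|
| 1 | 34.6% | 0.8 points |
| 3 | 37.2% | 2.5 points |
| 5 | 39.7% | 4.1 points |

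The arithmetic ceiling in Part 1 (all 27 SD patients moved) is 53/78 = 67.9%. It is a bound, not an estimate.

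For order of magnitude only, two assumptions are needed, neither from the documents:

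- 10% to 30% of the 122 patients are measurable in both serum and urine.
- 3.5% to 16.6% of those fall in the gap. These shares come from simulated log-normal best changes with serum–urine correlation 0.3 to 0.8 and the below-200 mg route included.

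This gives 122 × 0.10 × 0.035 = 0.4 patients up to 122 × 0.30 × 0.166 = 6.1 patients, or 0.35 to 5.0 points of CBR. The range leans high because it classifies one best change per patient. The SAP assesses every time point and reports best response, so a patient who passed through the MR range at an earlier visit is already in CBR. With six monthly visits and a gradual decline (also assumed), about 24% to 36% of gap patients had such a visit.

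**The case against.** The strongest reply is that this is not the sponsor's rule. Table 10 is presented as the published consensus criteria, and a footnote derives its MR definition from another consensus report. A CBR computed with the named standard is the CBR as defined. Interpretation questions are referred to the guideline, and the IRC assigns response under a charter that is not in these documents.

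The row also cannot be applied wholly literally. Eligibility allows disease measurable in one compartment only, yet a strict reading of the conjunction would bar a serum-only patient from MR altogether. An IRC that sensibly waives the urine part there may be equally sensible about the caps.

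The consequence is limited too. CBR has an interval and no test, and a few points are small beside it: for 41/122 = 33.6% the exact 95% CI is 25.3% to 42.7%. The disease control rate still counts these patients if SD lasts 12 weeks.

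Most of this stands, and it rules out two stronger readings. A reader might infer that the reported CBR is understated. That holds only against a floors-only definition and only if the IRC applies the caps mechanically, which the documents do not show. A reader might also infer a transcription error, but the source cannot be checked here.

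What does not stand is that the matter is already settled. Neither document says how a patient above MR in one compartment and short of PR is classed. Top-down assignment alone does not settle it, because once PR is excluded the caps still exclude the patient from MR.

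**Conclusion.** The point holds as a defect in the printed rule, not as a demonstrated bias. The MR and PR limits leave gaps at serum 49% to below 50% and urine between 89% and 90%. With both compartments capped and SD as the residual, some patients with larger reductions rank below patients with smaller ones.

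Any resulting effect on CBR is downward. It is probably small, at 0.8 points per patient at N=122, and the illustrative range above rests wholly on assumed inputs. The actual size depends on how many patients are measurable in both compartments and on IRC practice, neither of which the documents give. ORR and its test against 10% do not use MR and are unaffected. Correction is still worthwhile because CBR and duration of clinical benefit are named key secondary endpoints and the remedy is short.

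**What to change.** Keep the cited criteria and make three changes, set before the IRC adjudicates.

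1. **Close the boundaries.** In the MR row, make the serum upper limit below 50% and the urine upper limit below 90%. Leave the plasmacytoma condition as it is.
2. **Add a Table 10 footnote and matching IRC instruction.** Suggested text: *Categories are assigned from the top down. A patient who does not meet PR or better, but meets the MR floor in every measurable compartment (serum reduction of at least 25%; urine reduction of at least 50%) and the other MR conditions, is classed as MR.*
3. **Report the effect.** Give the number of patients classed as MR through this rule, and CBR with and without them.

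The cost is one table row, one footnote, one IRC instruction and one extra line in the CBR table. The downsides are a small, openly stated clarification to a cited table, and a check of Part 1 adjudications so that the pooled penta-refractory population (SAP 3.1.3) is classified by one rule. Because the clarification can only raise CBR in an open-label, single-arm trial, fixing it in advance and showing both figures guards against the appearance of a post hoc choice.

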## **APPENDIX 4. SELINEXOR FORMULATION AND ADMINISTRATION**

### **Description of Selinexor (KPT-330)**

Selinexor is a Selective Inhibitor of Nuclear Export (SINE) compound. Selinexor specifically blocks nuclear export by binding to the nuclear export protein XPO1.

*The chemical name is: (Z)-3-(3-(3,5-bis(trifluoromethyl)phenyl)-1H-1,2,4-triazol-1-yl)-N'-(pyrazin-2-yl)acrylohydrazide*

*The molecular formula is: C17H11F6N7O.*

*The molecular weight is: 443.31*

### **Form**

Selinexor will be supplied and administered as 20 mg, coated, immediate-release tablets.

### **Storage and Stability**

Selinexor tablets (20 mg) will be supplied in plastic film blisters with an aluminum foil lidding packaged in a secondary paper wallet with childproofing. Selinexor should be stored in a locked and secured area with access restricted to the site staff pharmacist or designee(s), with temperature at or below 30°C (86°F). Room temperature storage is recommended, refrigerated is suitable. Tablets should not be stored frozen.

Selinexor tablets are currently in on-going stability studies. The expiry will be based on concurrent stability studies and extended during the course of the study as further stability data becomes available.

### **Handling**

Qualified personnel, familiar with procedures that minimize undue exposure to themselves and the environment, should undertake the preparation, handling, and safe disposal of the chemotherapeutic agent in a self-contained and protective environment.

### **Availability**

Selinexor is an investigational agent and will be supplied free-of-charge from Karyopharm Therapeutics Inc.

### **Preparation**

No special preparation required.

NOTE: Tablets of selinexor should not be crushed because of increased risk of dermatologic toxicity if powder comes in contact with skin.

### **Administration**

Selinexor will be provided as tablets for oral administration. Selinexor is to be taken within 30 minutes of solid food consumption together with at least 120 mL (4 ounces) of fluids (water, milk, etc.).

Patients in the present study will receive selinexor 80 mg (45 mg/m^2 BSA) plus dexamethasone (20 mg), both twice weekly, during Weeks 1-4 of each four-week cycle.

### **Accountability**

The Investigator, or a responsible party designated by the Investigator, must maintain a careful record of the inventory and disposition of the agent (investigational or free of charge) using the NCI Drug Accountability Record or another comparable drug accountability form. (see the Cancer Therapy Evaluation Program [CTEP] website at <http://ctep.cancer.gov/protocolDevelopment> for the “Policy and Guidelines for Accountability and Storage of Investigational Agents” or to obtain a copy of the drug accountability form).

### **Destruction and Return**

At the end of the study, unused supplies of selinexor should be destroyed according to institutional policies. Destruction will be documented in the Drug Accountability Record Form.

## APPENDIX 5. LENS OPACITIES CLASSIFICATION SYSTEM

For patients enrolled under protocol version 3.0, if a cataract is seen during the slit lamp examination to document lens clarity, the cataract will be graded according to the grading system shown below.

**Table 11: Lens Opacities Classification System**

Grading of Cataracts*				
Cataract Type	Grade 1	Grade 2	Grade 3	Grade 4
Nuclear Yellowing and sclerosis of the lens nucleus	Mild	Moderate	Pronounced	Severe
Cortical Measured as aggregate percentage of the intrapupillary space occupied by the opacity	Obscures 10% of intrapupillary space	Obscures 10% -50% of intra-pupillary space	Obscures 50% -90% of intra-pupillary space	Obscures >90% of intrapupillary space
Posterior subcapsular Measured as the aggregate percentage of the posterior capsular area occupied by the opacity	Obscures 10% of the area of the posterior capsule	Obscures 30% of the area of the posterior capsule	Obscures 50% of the area of the posterior capsule	Obscures >50% of the area of the posterior capsule
*Designation of cataract severity that falls between grade levels can be made by addition of a + sign (e.g., 1+, 2+). Grading of cataracts is usually done when pupil is dilated.				

Source: Optometric Clinical Practice Guideline: Care of the Adult Patient with Cataracts (CPG8). American Optometric Association at [www.aoa.org](http://www.aoa.org).

**APPENDIX 6. GLUTATHIONE (GSH)-, S-ADENOSYLMETHIONINE (SAM)-, OR N-ACETYLCYSTEINE (NAC)-CONTAINING PRODUCTS (REPRESENTATIVE LIST)**

**Table 12: Glutathione (GSH)-, S-Adenosylmethionine (SAM)-, OR N-Acetylcysteine (NAC)-Containing Products (Representative List)**

Glutathione (GSH)		N-acetylcysteine (NAC)		S-adenosylmethionine (SAM)	
Product Name	Ingredient	Product Name	Ingredient	Product Name	Ingredient
Glutathione	glutathione	Antidote for acetaminophen overdose	acetylcysteine	SAM-e Complete	S-adenosyl-methionine
L-Glutathione	L-glutathione	Cerefolin NAC: medical food for age-related memory loss	L-methylfolate vitamin B12 N-acetyl cysteine	SAMe	S-adenosyl-L-methionine
Glutathione reduced	glutathione	NAC	N-acetyl cysteine	Double Strength SAMe 400	S-adenosyl-methionine
Reduced glutathione with alpha lipoic acid	Setria L-glutathione	N-A-C Sustain	N-acetyl L-cysteine		
Glutathione, Cysteine & C	glutathione L-cysteine vitamin C	Best NAC Detox Regulators	N-acetyl cysteine		
(Mega-) Liposomal Glutathione	glutathione				
Lypospheric GSH	glutathione				
Ivory Caps Skin Enhancement Formula	glutathione				

## APPENDIX 7. SUMMARY OF CHANGES

### Amendment 1

#### Amendment Rationale

The primary purpose for this amendment is to:

- Address the following FDA deficiency and comments provided in an e-mail message with the subject: “IND-114042 KPT-330-Deficiency and Comments”, dated: 21Jan2014:
  - Deficiency:
    - To be eligible for the trial, patients should have returned to  $\leq$  Grade 2 non hematological toxicities from previous treatment.
  - Comments:
    - The primary endpoint should be per central independent review committee including radiology review.
    - Time-to-event endpoints such as PFS/OS and Patient Reported Outcomes are not evaluable in non-controlled trials.

The revised protocol Version 2.0, dated 05Feb2015 will be submitted by the Principal Investigator(s) to all applicable Institutional Review Boards (IRBs), Independent Ethics Committees (IECs), or Research Ethics Boards (REBs), and by Karyopharm Therapeutics Inc. to all applicable Regulatory Authorities.

A summary of key changes that were made to protocol Version 1.0, including rationales for these changes, is provided below.

#### Changes to the Protocol

##### Administrative Changes

- Internal changes to improve clarity and eliminate inconsistencies between sections (**Modified sections:** Global)
- Updated the version number and date of protocol from Version 1.0 dated 15 Apr 2014 to Version 2.0 dated 05 Feb 2015 (**Modified sections:** Global)

##### Specific Content Changes

#### Synopsis

##### Table 1.1

- Changed the Screening Period from 14 days to 21 days prior to C1 D1
- Removed mention of randomization

##### Section 7.2 Data Monitoring Committee

- Added sub-sections to clarify the roles of the DMC for reviewing safety and response data (the latter was added in response to comments by the FDA).

##### Section 8.3 Inclusion Criteria

- Added resolution of hematologic toxicities from previous treatments to  $\leq$  Grade 2 in response to a deficiency reported by the FDA

**Section 9.2.5 Survival Follow-Up**

- SPEP, UPEP and FLC every 3 months to assess durability of response was added to be consistent with the SOA

**Section 10.5 Skeletal Survey**

- Modified to include central read.

**Section 10.8 Pharmacokinetic Endpoints**

- Table 10.1 was revised to reflect PK CCI

**Section 12.4 Concomitant Treatments**

- Redundant wording for restricted medications was deleted

**Section 14.3.4 Secondary Endpoints**

- Text was revised to clarify that PFS, QoL and OS will not be tested for statistical significance, in response to comments from the FDA.

## Amendment 2

### Amendment Rationale

The primary purposes for this amendment were to:

1. Revise the study target patient population from “quad-refractory” to “dual-refractory” as shown in the following modified inclusion criteria:

*From:* Patients must have “MM refractory to lenalidomide, pomalidomide, bortezomib, and carfilzomib.”

*To:* “Patients must have been previously exposed to lenalidomide, pomalidomide, bortezomib, and carfilzomib” *and have* “MM double refractory to previous treatment with both the PI and IMiD drug classes”

2. Change the study treatment (selinexor plus dexamethasone) dose schedule from “twice weekly for three weeks of every four-week cycle” to “twice weekly for every week of each four-week cycle.”

The revised protocol Version 3.0, dated 25 September 2015 will be submitted by the Principal Investigator(s) to all applicable Institutional Review Boards (IRBs), Independent Ethics Committees (IECs), or Research Ethics Boards (REBs), and by Karyopharm Therapeutics Inc. to all applicable Regulatory Authorities.

A summary of key changes that were made to protocol Version 2.0, including rationales for these changes, is provided below.

### Changes to the Protocol

#### Administrative Changes

- Revisions were made to harmonize procedures and assessments with those in clinical protocol KCP-330-017 (STOMP): A Phase 1b/2 Study of Selinexor (KPT-330) in Combination with Backbone Treatments for Resistant/Refractory Multiple Myeloma.
- Internal changes were made to improve clarity and eliminate inconsistencies across sections (**Modified sections:** Global)
- Updated the version number and date of protocol from Version 2.0 dated 05 February 2015 to Version 3.0 dated 25 September 2015 (**Modified sections:** Global)

#### Specific Content Changes

##### Title

*From:* A Phase 2b, Open-Label, Single-Arm Study of Selinexor (KPT-330) plus Low-Dose Dexamethasone in Patients with Multiple Myeloma Quad-refractory to Previous Therapies

*To:* A Phase 2b, Open-Label, Single-Arm Study of Selinexor (KPT-330) plus Dexamethasone in Patients with Multiple Myeloma Double-refractory to Previous Therapies

